APPENDIX I: WHO classification and criteria for the myelodysplastic syndromes (MDS)

| Disorder | Peripheral Blood | Bone Marrow |
|---|--|--|
| Refractory Anemia (RA) | Anemia No or rare blasts | Erythroid dysplasia only <5 percent blasts <15 percent ringed sideroblasts |
| Refractory Anemia with Ringed Sideroblasts (RARS) | Anemia No blasts | Erythroid dysplasia only <5 percent blasts ≥15 percent ringed sideroblasts |
| Refractory Cytopenia with Multilineage Dysplasia (RCMD) | Bi- or pan-cytopenia No or rare blasts No Auer rods Monocytes <1,000/µL | Dysplasia in ≥10 percent of cells in two or more myeloid cell lines No Auer rods <5 percent blasts <15 percent ringed sideroblasts |
| Refractory Cytopenia with Multilineage Dysplasia and Ringed Sideroblasts (RCMD-RS) | Bi- or pan-cytopenia No or rare blasts No Auer rods Monocytes <1,000/µL | Dysplasia in ≥10 percent of cells in two or more myeloid cell lines No Auer rods <5 percent blasts ≥15% ringed sideroblasts |
| Refractory Anemia with Excess Blasts-1 (RAEB-1) | Cytopenias <5% blasts No Auer rods Monocytes <1,000/µL | Unilineage or multilineage dysplasia 5-9 percent blasts No Auer rods |
| Refractory Anemia with Excess Blasts-2 (RAEB-2) | Cytopenias 5-19% blasts Auer rods ± Monocytes <1,000/µL | Unilineage or multilineage dysplasia 10-19 percent blasts Auer rods ± |
| MDS-Unclassified (MDS-U) | Cytopenias No or rare blasts No Auer rods | Unilineage dysplasia in granulocytes or megakaryocytes No Auer rods <5 percent blasts |
| MDS with del(5q) "5q- syndrome" | Anemia <5 percent blasts Platelets usually normal or increased | Normal to increased megakaryocytes with hypolobulated nuclei No Auer rods <5 percent blasts Isolated del(5q) |

APPENDIX II: Performance Status Scales

| ECOG Performance Status Scale | | Karnofsky Performance Scale | |
|-------------------------------|---|-----------------------------|--|
| Grade | Descriptions | Percent | Description |
| 0 | Normal activity. Fully active, able to carry on all pre-disease performance without restriction. | 100 | Normal, no complaints, no evidence of disease. |
| | | 90 | Able to carry on normal activity; minor signs or symptoms of disease. |
| 1 | Symptoms, but ambulatory. Restricted in physically strenuous activity, but ambulatory and able to carry out work of a light or sedentary nature (e.g., light housework, office work). | 80 | Normal activity with effort; some signs or symptoms of disease. |
| | | 70 | Cares for self, unable to carry on normal activity or to do active work. |
| 2 | In bed <50% of the time. Ambulatory and capable of all self-care, but unable to carry out any work activities. Up and about more than 50% of waking hours. | 60 | Requires occasional assistance, but is able to care for most of his/her needs. |
| | | 50 | Requires considerable assistance and frequent medical care. |
| 3 | In bed >50% of the time. Capable of only limited self-care, confined to bed or chair more than 50% of waking hours. | 40 | Disabled, requires special care and assistance. |
| | | 30 | Severely disabled, hospitalization indicated. Death not imminent. |
| 4 | 100% bedridden. Completely disabled. Cannot carry on any self-care. Totally confined to bed or chair. | 20 | Very sick, hospitalization indicated. Death not imminent. |
| | | 10 | Moribund, fatal processes progressing rapidly. |
| 5 | Dead. | 0 | Dead. |

Lansky Play Performance Status Scale

| Lansky Play Performance Scale | |
|-------------------------------|--|
| Score | Description |
| 100 | Fully active, normal |
| 90 | Minor restrictions in physically strenuous activity |
| 80 | Active, but tires more quickly |
| 70 | Both, greater restrictions of, and less time spend in play activities |
| 60 | Up and around, but minimal active play, keeps busy with quieter activities |
| 50 | Gets dressed but lies around much of the day, no active play; able to participate in |
| 40 | Mostly in bed; participates in quiet activities |
| 30 | In bed; needs assistance even for quiet play |
| 20 | Often sleeping; play entirely limited to very passive activities |
| 10 | Unresponsive |
| 0 | Dead |

APPENDIX III: The Hematopoietic Cell Transplant-Comorbidity Index (HCT-CI)

Instructions: Circle applicable scores and provide actual value or cause of co-morbidity.

| Comorbidities | Definitions | HCT-CI weighted scores | Actual Lab Values/Comments |
|---|--|------------------------|----------------------------|
| Arrhythmia | Atrial fibrillation or flutter, sick sinus syndrome, and ventricular arrhythmias | 1 | |
| Cardiac | Coronary artery disease‡, congestive heart failure, myocardial infarction, or EF<50% | 1 | |
| Inflammatory bowel disease | Crohn's disease or ulcerative colitis | 1 | |
| Diabetes* | Requiring treatment with insulin or oral hypoglycemics, but not diet alone | 1 | |
| Cerebro-vascular disease | Transient ischemic attack or cerebro-vascular Accident | 1 | |
| Psychiatric Disturbance | Depression anxiety requiring psychiatric consult or treatment | 1 | |
| Hepatic -mild* | Chronic hepatitis, Bilirubin >ULN- 1.5 X ULN, or AST/ALT >ULN-2.5XULN | 1 | |
| Obesity* | Patients with a body mass index > 35kg/ m ² | 1 | |
| Infection* | Requiring continuation of anti-microbial Treatment after day 0 | 1 | |
| Rheumatologic | SLE, RA, polymyositis, mixed CTD Polymyalgia rheumatica | 2 | |
| Peptic ulcer* | Requiring treatment | 2 | |
| Moderate/severe renal* | serum creatinine>2mg/dl, on dialysis, or prior renal transplantation | 2 | |
| Moderate pulmonary* | DLCO and/or FEV, >65%-80% or Dispend on slight activity | 2 | |
| Prior solid tumor | Treated at any time point in the patient's past history, excluding non-melanoma skin cancer | 3 | |
| Heart valve disease* | Except mitral valve prolapse | 3 | |
| Severe pulmonary* | DLCO and/or FEV ₁ <65% or Dyspnea at rest requiring oxygen | 3 | |
| Moderate/severe Hepatic | Liver cirrhosis, Bilirubin>1.5XULN or AST/ALT>2.5XULN | 3 | |
| Please provide Karnofsky performance Score= _____ % (KPS): | | Total Score = _____ | |

Completed by (print): _____ Date _____
completed: _____

Signature: _____

*Comorbidity is currently active or patient requires medical treatment +

‡One or more vessel-coronary artery stenosis, requiring medical treatment, stent, or bypass graft

2275.00

EF indicates ejection fraction; ULN, upper limit of normal; SLE, systemic lupus erythematosus; RA, rheumatoid arthritis; CTD, connective tissue disease;
DLCO, diffusion capacity of carbon monoxide; FEV₁, forced expiratory volume in one second; AST, aspartate aminotransferase; ALT, alanine aminotransferase

APPENDIX IV: Guidelines for Total Body Irradiation

All patients who have had previous radiation therapy or TBI should be seen by Radiation Oncology prior to entrance on the protocol for approval for additional TBI. TBI may be delivered by local guidelines provided the effective dose is equivalent to what is recommended in the TBI Guidelines.

Patients ineligible for this protocol include those who have had previous irradiation to areas of the body such that the Radiation Oncologist feels that even a relatively small dose of total body irradiation (TBI) cannot safely be given.

For patients previously exposed to total body irradiation (TBI), the Radiation Oncologist will determine whether the patient can safely receive additional TBI based on prior exposure history. In addition, the treating Radiation Oncologist, along with the attending physician, will determine the need for lung and/or kidney shielding from the radiation beam to prevent excessive toxicity and again based on the history of exposure. No other organs may be shielded.

TBI dosing guidelines

Dose level 1:

The treatment dose regimen will be 200 cGy in one fraction. No lung shielding or kidney shielding will be used for this TBI scheme unless patients have experienced previous irradiation (see lung shielding below).

Dose level 2:

The second dose level will be 300 cGy in one fraction for the first TBI dose level. No lung shielding or kidney shielding will be used for this TBI scheme unless patients have experienced previous irradiation (see lung shielding below).

Dose level 3:

The third dose level will be 400 cGy in one fraction. Lung shielding will be used for this TBI scheme as outlined below.

Dose level 4:

The fourth dose level will be 450 cGy in one fraction for patients > 7 years old. Patients ≤ 7 years old will receive 225 cGy BID over one day. Lung shielding will be used for this TBI scheme as described below.

Modality:

High-energy photons with energy $\geq 6\text{MV}$ photons should be utilized. Although there is no upper limit on the energy as long as the skin dose requirements can be met, it is recommended that 18MV or lower be used. The selection of energy is determined by the dose uniformity criterion.

Target Volume:

The total body will be treated including the head and feet in one field (except in certain circumstances). Care should be taken to ensure that the patient is entirely within the 90% isodose decrement line of the beam (i.e., not in the penumbra region of the beam).

Target Dose:

The prescription point is defined as the point along the longitudinal axis of the patient at the midline at the level of the umbilicus (see Prescription **Point 2**). No tissue inhomogeneity correction will be made in the calculation of dose to the prescription point. The absorbed dose along the patient's head to toe axis (line formed by the intersection of the midsagittal plane and the midcoronal plane) shall be within 10% of the prescribed dose. The dose at selected anatomical points shall be calculated and these calculations are to be submitted as part of the quality assurance. Measurements of patient dimensions needed for the calculation of the prescription dose will be made at the time of the simulation for lung blocks.

Measurement and calculations of required monitor units may be necessary for each treatment and will be performed for both the expected upright treatment position (AP-PA fields) and the reclining, lateral decubitus position (AP-PA fields) or lateral field techniques. Pediatric patients may be treated prone and supine under anesthesia by AP-PA fields. In the event the patient proves too ill to receive a fraction in the upright position, dose calculation may be pre-calculated to permit treatment in the lateral decubitus position).

Dose point calculations:

1. **Head (Point 1):** this reference point is defined along the longitudinal axis of the skull at the greatest mid-separation (immediately superior to the nasal bridge). The depth should be taken as midway between the entrance and exit points of the opposed radiation beams.
2. **Neck (Point 2):** this reference point is defined along the patient's longitudinal axis at the level of C3/C4 (approximate mid-neck, but chosen for the thinnest mid-separation of the neck). The point is taken to be midway between the entrance and exit point of the beam.
3. **Upper Mediastinum (Point 3):** this reference point is defined along the patient's longitudinal axis at the level of the angle of Louis. The reference point is midway between the entrance and the exit points of the opposed beams.
4. **Lower Mediastinum (Point 4):** this reference point is defined along the patient's longitudinal axis at the level of the xiphisternal notch. The reference point is midway between the entrance and exit points of the opposed beams
5. **Umbilicus (Point 5):** THE PRESCRIPTION POINT is defined along the patient's longitudinal axis at the level of the umbilicus. The prescription point is midway between the entrance and exit points of the opposed beams.
6. **Knee (Point 6):** this reference point is defined along the midline in the midplane of the knee at the level of the patella.
7. **Ankle (Point 7):** this reference point is defined along the midline at the midplane of the ankle at the level of the lateral malleolus.
8. **Shielded Lung Dose (Point 8):** this reference point is located on the right chest wall under the lung block. It is centered (both medial/lateral and cephalocaudad) under the lung block as projected on the patient's skin. The depth should be taken as midway between the entrance and exit points of the opposed radiation beams. Dose measurements at this location will be taken during a fraction with lung shielding in place.

9. Unshielded Lung Dose (Point 9): This reference point is the same as point 8. Dose measurements at this location will be taken during a fraction without lung shielding in place. The depth should be taken as midway between the entrance and exit points of the opposed radiation beams.

Prescription Points/Dose Monitoring Points:

- 1. Head (Point 1):** this prescription point/dose monitoring point is defined along the longitudinal axis of the skull at the greatest mid-separation (immediately superior to the nasal bridge). The depth should be taken as midway between the entrance and exit points of the opposed radiation beams. Prescription point measured each fraction AP/PA.
- 2. Umbilicus (Point 2):** the prescription point/dose monitoring point is defined along the patient's longitudinal axis at the level of the umbilicus. The prescription point is midway between the entrance and exit points of the opposed beam. Prescription point measured each fraction AP/PA.
- 3. Ankle (Point 3):** this dose monitoring point is defined along the midline at the midplane of the ankle.

Dose Definition:

The absorbed dose is specified as centigray (cGy)-to-muscle.

Dose Rate:

A mid-plane dose rate of between 6 and 15 cGy per minute is required.

Dose Uniformity:

The objective is to keep the dose throughout the body, defined to extend to within 2 mm of the skin surface, to at least 90% of the prescription dose. In addition, the brain dose shall not exceed 107% of the prescription dose. For some AP/PA treatments, partial transmission lung blocks will be used to limit the overall total lung dose. The dose at the midpoint of the thickest part of the body while in the treatment position should be determined and if necessary, modifications made to the treatment to raise the dose in this region to at least 90% of the prescription dose.

In order to satisfy the requirement that the skin dose at a depth of 2 mm is within at least 90% of the prescription dose, beam spoilers or other equally effective devices should be used. The field size shall be such that no part of the patient extends into the portion of the penumbra region where the dose is less than 90% of the central axis dose.

Treatment Technique:

Patients will be treated using AP/PA fields in an upright seated or standing position in a TBI positioning device. Treatment will be delivered with equally weighted parallel opposed portals, with each treatment including both AP and PA fields. If the patient is unable to tolerate the upright position, acceptable alternate arrangements will include equally weighted AP-PA or lateral parallel opposed fields delivered to the patient in a lateral decubitus position on a treatment couch or gurney.

Changes in patient positioning after the patient has started TBI are discouraged. When unavoidable, to ensure compliance to the overall dose and lung shielding parameters, appropriate

changes in lung blocking and dose recalculation will be required. Young patients requiring anesthesia will be treated in an AP/PA configuration at extended distance.

Dose Calculation for the Prescription Point:

The calculation of the treatment time or the monitor units for the prescribed dose can be carried out using standard techniques. However, TBI presents special problems relative to the routine treatment situation in that the field sizes are much larger and the treatment distances much longer. The TBI percent depth dose (PDD) or Tissue Maximum Ratio (TMR) and output factors should be measured under TBI treatment conditions for a range of phantom sizes to establish the database for TBI beam-on time calculations or to validate the calculation methodology.

Typically, a calculation methodology will be adopted which uses PDD or TMR and output factors measured under standard conditions but then modified to account for the larger treatment distance. For example, modified values for inverse square corrected percentage depth dose or tissue-air ratios and tissue phantom ratios are necessary for some treatment units when the patient is positioned at a long distance from the photon source and near the floor or one wall of the room. Also, some deviation from an exact inverse square decrease with distance has been demonstrated for certain geometries.

Measurements of dose at the center of a phantom about the size of the typical patient should be performed and compared to the calculated dose. If differences are found, additional correction factors should be introduced to the calculation method.

Critical Organ Dose Points:

The required dose calculations should be performed for at least 3 points referenced above, including the dose monitoring points. The midline dose at these locations should be recorded on the TBI Summary Form. The dose can be calculated based on the thickness at each location and factors appropriate to the TBI treatment conditions.

It is recommended that entrance and exit TLDs or diodes be placed on the patient at each required dose assessment location. The midline dose can be calculated from these measurements making the appropriate corrections to the readings and then averaging the corrected values. In younger patients it is also recommended that TLDs or diodes be placed underneath the lung blocks to document the transmission dose and scatter dose.

Lung Shielding:

Lung shielding shall be used in all patients who receive a dose ≥ 400 cGy total TBI. One half value layer transmission (HVL) blocks will be used for **Dose Levels 3 and 4**. In addition, for patients receiving 200 or 300 cGy of TBI who have received previous irradiation, the treating Radiation Oncologist will determine whether the patient can safely receive additional TBI based on prior exposure history. In addition, the treating Radiation Oncologist, along with the attending physician, will determine the need for lung and/or kidney shielding from the radiation beam to prevent excessive toxicity and again based on the history of exposure. If the lungs should be shielded, one half value layer lung blocks will be used to decrease the photon contribution to the lung dose to approximately half that of the prescription point.

In the event that the Radiation Oncologist feels it is necessary, one half value layer POSTERIOR kidney blocks may be used to decrease the photon contribution to the kidneys to approximately 75% that of the prescription point.

Lung-Block Design:

Lung blocks will confirm to the following guidelines: The lateral edges will be 1.0 – 1.5 cm from the inner border of the ribs; the inferior edges will be 1.0 – 1.5 cm from the dome of the apex of the diaphragm; the superior borders will be 1.0 – 1.5 cm below the clavicles; the medial border 2.0 – 2.5 cm from the lateral edges of the thoracic vertebral bodies. No contouring of the lung shields will be done around the hilum unless there is a residual abnormal hilar adenopathy, in which case the margins around the hilar mass will be 1.0 – 1.5 cm.

Lung-Block Timing:

Lung blocks will be employed for the treatment(s) listed below. Should patient infirmity preclude upright positioning during a fraction when lung shielding is prescribed, that patient may be treated in the lateral decubitus position without lung shielding, and lung shielding can be deferred until the next treatment fraction. For children receiving TBI under anesthesia, treatments will be performed in a modified supine and prone position, with the appropriate lung shielding as specified in the protocol.

Lung blocks will be used for the first fraction of the first incremental dose escalation over 300 cGy, i.e., 400 cGy for one fraction, or 450 cGy for one fraction, or both fractions for pediatric patients treated with 225 cGy x 2. This schema is calculated to deliver a nominal dose of approximately 200 cGy for **Dose Level 3** ($400 \times 50\% = 200$); and 225 cGy for **Dose Level 4** ($450 \times 50\% = 225$ cGy). No compensatory electron boost of that portion of the chest wall shielded by the lung blocks is required.

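### At 400 and 450 cGy, each given in one fraction, the clause deferring lung shielding to a later fraction omits mandatory shielding and doubles the nominal lung dose

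*Combined protocol and SAP*

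**What the plan says.** Appendix IV sets four TBI dose levels. Level 1: "The treatment dose regimen will be 200 cGy in one fraction". Level 2: "The second dose level will be 300 cGy in one fraction". Level 3: "The third dose level will be 400 cGy in one fraction". Level 4 is 450 cGy, as a single fraction for patients over 7 years and as two fractions of 225 cGy on one day for those aged 7 or under. That makes five schedules, of which only the last has more than one fraction.

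The Lung Shielding paragraph of the same appendix states: "Lung shielding shall be used in all patients who receive a dose" of 400 cGy or more in total. It specifies half-value-layer blocks for levels 3 and 4. At levels 1 and 2 the default is the reverse: "No lung shielding or kidney shielding will be used for this TBI scheme unless patients have experienced previous irradiation". For those patients the Radiation Oncologist and the attending physician decide case by case, and "If the lungs should be shielded, one half value layer lung blocks will be used".

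Lung-Block Timing opens by referring to a list of treatments in which blocks are used. The list names the single 400 cGy fraction, the single 450 cGy fraction, and both fractions of 225 cGy x 2. The same subsection says that a patient who cannot be upright for a fraction with prescribed shielding may be treated in lateral decubitus without it, and that "lung shielding can be deferred until the next treatment fraction".

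Section 8.A still lists 300, 400 and 450 cGy as escalation steps. Section 14 says that the escalation rule for excess graft failure no longer applies in the modified protocol.

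**The concern.** Deferral presupposes a later fraction in which the shielding can be given. At 400 cGy and at 450 cGy in one fraction there is none, so a site that follows the clause leaves out shielding that the preceding paragraph makes compulsory. The wording suggests that the shielding will still be given, and the clause asks nobody to accept the unshielded dose.

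At stake is the lung dose of an individual patient who is already too unwell to stand or sit for treatment. No sample size, error rate or analysis is involved.

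**Working it through.** **Inputs, all from Appendix IV.** Fraction doses and counts come from the dose-level text. Block transmission is about 50% (Lung Shielding; also used in the calculation under Lung-Block Timing).

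**Formula.** Nominal lung dose = sum over fractions of (fraction dose x 0.5 if blocked, x 1 if not).

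**The plan's own figures.** Level 3: 400 x 0.5 = 200 cGy. Level 4: 450 x 0.5 = 225 cGy. Both match Lung-Block Timing. The two-fraction version of level 4 gives 112.5 + 112.5 = 225 cGy, the same nominal dose.

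**With the clause used at one fraction:**

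| Schedule | Blocks | All fractions blocked (cGy) | One fraction unblocked (cGy) | Ratio |
|---|---|---|---|---|
| 400 x 1 | mandatory | 200 | 400 | 2.0 |
| 450 x 1 (over 7 years) | mandatory | 225 | 450 | 2.0 |
| 225 x 2 (7 years or under) | mandatory, both fractions | 225 | 225 + 112.5 = 337.5 | 1.5 |
| 200 x 1 | only if ordered after previous irradiation | 100 | 200 | 2.0 |
| 300 x 1 | only if ordered after previous irradiation | 150 | 300 | 2.0 |

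**Is there a fraction to defer to?**

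- *400 and 450 cGy in one fraction.* None remains after the treated one. Both schedules are on the Lung-Block Timing list and shielding is mandatory, so this result does not depend on how the clause is read.
- *225 cGy x 2.* If blocks are missed at the first fraction, a second follows, but it must be blocked anyway, so nothing is made up and the total is 337.5 cGy. If they are missed at the second, nothing follows. If they are missed at both, the lung dose is 225 + 225 = 450 cGy, or 2.0 times the nominal dose.
- *200 and 300 cGy.* None remains. Whether the clause reaches these doses depends on whether its condition, a fraction with prescribed shielding, includes blocks ordered "for patients receiving 200 or 300 cGy of TBI who have received previous irradiation". The list does not name these doses.

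**Does other text supply the missing fraction?** Four provisions could be thought to:

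- The introduction to Appendix IV allows local guidelines if the effective dose is equivalent; this adds no fraction.
- Target Dose allows calculations for lateral decubitus to be made in advance; this prepares the unshielded treatment but does not replace the blocks.
- Point 9, under the dose-point definitions, measures lung dose in a fraction without shielding; it documents the dose and does not reduce it.
- Treatment Technique asks for changed blocking and recalculation when position changes after TBI has begun, so that the shielding parameters are still met; this points away from the deferral clause.

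**The case against.** The strongest reply concerns breadth. A reader might infer that the clause fails equally in all four single-fraction schedules. The documents do not settle that: 200 and 300 cGy are absent from the Lung-Block Timing list, and optional blocks at those doses are dealt with elsewhere in the appendix. The text is clearest at 400 and 450 cGy, but those are escalated levels whose escalation rule Section 14 withdraws. The one dose independent of escalation, 200 cGy, is where the reading is open. This stands, and it is why 200 and 300 cGy are secondary here.

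A reader might also infer that the clause flatly contradicts the both-fractions rule at 225 cGy x 2. Its wording is permissive and can be taken as an exception for infirm patients. Children under anesthesia have their own sentence, which keeps shielding in supine and prone positions, so few patients would come under the clause at this schedule. That also stands. What remains is that, even as an exception, it cannot work as a deferral, because the second fraction has no spare shielding to give.

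Safeguards exist: selected-point dose calculations are submitted for quality assurance, Point 9 anticipates an unshielded fraction, and shielding at 200 and 300 cGy is already decided individually. They weaken any picture of an unnoticed dose, but they do not restore the blocks.

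Finally, the proposed sentence may leave the dose unchanged where blocks cannot be used. The appendix allows AP-PA fields in lateral decubitus but does not describe blocks in that position. This is correct, and no guaranteed dose reduction is claimed.

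**Conclusion.** The point holds for 400 cGy and for 450 cGy in one fraction. The clause defers mandatory shielding to a fraction that does not exist, and the nominal lung dose becomes 400 instead of 200 cGy, or 450 instead of 225 cGy. The figures assume the appendix's approximate 50% transmission.

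Two cases are secondary and depend on the reading: 225 cGy x 2 (337.5 against 225 cGy with one fraction missed), and 200 or 300 cGy with blocks ordered after previous irradiation (200 against 100, 300 against 150 cGy).

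Reach is small. The patient must be unable to be upright, and the documents do not say which TBI level is in use. A reader might infer from a doubled dose that lung toxicity or day-200 non-relapse mortality would rise. The documents give no dose-response relation and no count of affected patients, so these remain dose ratios only. Severity is minor.

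**What to change.** In Appendix IV, Lung-Block Timing, replace the sentence on infirm patients with:

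> Lung shielding is not deferred. If a patient is too infirm to be upright for a fraction for which lung blocks are prescribed, treatment is given in an alternate position with AP-PA fields and lung blocks where feasible. If blocks cannot be used, the treating Radiation Oncologist records, before that fraction, the decision to treat without them and the expected lung dose.

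The existing TBI Summary Form could hold the record. If the escalated TBI levels have been retired along with the escalation rule, delete them from Section 8.A and Appendix IV.

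The cost is one replaced sentence and one recorded decision for each patient who cannot be shielded, plus text deletions if levels are retired. No visit or procedure is added. Where blocks are not feasible the dose stays the same, but someone responsible has accepted it explicitly.
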